4.3.3 Supportive Care Guidelines

Subjects should receive appropriate supportive care measures as deemed necessary by the treating investigator, including medications for management of rituximab-related infusion reactions which may be administered per institutional standard of care.

Suggested supportive care measures for the management of adverse events with potential immunologic etiology are outlined below. Where appropriate, these guidelines include the use of oral or intravenous treatment with corticosteroids as well as additional anti-inflammatory agents if symptoms do not improve with administration of corticosteroids. Note that several courses of steroid tapering may be necessary as symptoms may worsen when the steroid dose is decreased. For each disorder, attempts should be made to rule out other causes such as metastatic disease or bacterial or viral infection, which might require additional supportive care. The treatment guidelines are intended to be applied when the investigator determines the events to be related to pembrolizumab.

Note: if after the evaluation the event is determined not to be related, the investigator does not need to follow the treatment guidance (as outlined below). Refer to Table 4 for dose modification.

It may be necessary to perform conditional procedures such as bronchoscopy, endoscopy, or skin photography as part of evaluation of the event.

When study interventions are administered in combination, attribution of an adverse event to a single component is likely to be difficult. Therefore, while the investigator may attribute a toxicity event to pembrolizumab alone, to rituximab alone, to obinutuzumab alone, or to the combination, for adverse events listed below, all interventions must be held according to the criteria below.

When study interventions are administered in combination, if the AE is considered immunerelated, all interventions should be held according to recommended dose modifications.

Participants may not have any dose modifications (no change in dose or schedule) of pembrolizumab in this study.

- If the toxicity does not resolve or the criteria for resuming treatment are not met, the participant must be discontinued from all study interventions.
- If the toxicities do resolve and conditions are aligned with what is defined below, the combination of study therapies may be restarted at the discretion of the investigator. In these cases where the toxicity is attributed to the combination or to rituximab or obinutuzumab alone, re-initiation of pembrolizumab as a monotherapy may be considered at the investigator's discretion.

• Pneumonitis:

- a. For **Grade 2 events**, treat with systemic corticosteroids. When symptoms improve to Grade 1 or less, steroid taper should be started and continued over no less than 4 weeks.
- b. For **Grade 3-4 events**, immediately treat with intravenous steroids. Administer additional anti-inflammatory measures, as needed.
- c. Add prophylactic antibiotics for opportunistic infections in the case of prolonged steroid administration.
- d. For recurrent grade 2 or grade 3-4 pneumonitis, permanently discontinue pembrolizumab.

• Diarrhea/Colitis:

Subjects should be carefully monitored for signs and symptoms of enterocolitis (such as diarrhea, abdominal pain, blood or mucus in stool, with or without fever) and of bowel perforation (such as peritoneal signs and ileus).

- a. All subjects who experience diarrhea/colitis should be advised to drink liberal quantities of clear fluids. If sufficient oral fluid intake is not feasible, fluid and electrolytes should be substituted via IV infusion. For Grade 2 or higher diarrhea, consider GI consultation and endoscopy to confirm or rule out colitis.
- b. For Grade 2 diarrhea/colitis, administer oral corticosteroids.
- c. For **Grade 3 or 4 diarrhea/colitis**, treat with intravenous steroids followed by high dose oral steroids.
- d. When symptoms improve to Grade 1 or less, steroid taper should be started and continued over no less than 4 weeks.
- Type 1 diabetes mellitus (if new onset, including diabetic ketoacidosis [DKA]) or ≥ Grade 3 Hyperglycemia, if associated with ketosis (ketonuria) or metabolic acidosis (DKA)
- a. For **T1DM** or **Grade 3-4** Hyperglycemia Protocol v4.0 dated 21 July 2021

- i. Insulin replacement therapy is recommended for Type I diabetes mellitus and for Grade 3-4 hyperglycemia associated with metabolic acidosis or ketonuria.
- ii. Evaluate patients with serum glucose and a metabolic panel, urine ketones, glycosylated hemoglobin, and C-peptide.

• Hypophysitis:

- a. For **Grade 2** events, treat with corticosteroids. When symptoms improve to Grade 1 or less, steroid taper should be started and continued over no less than 4 weeks. Replacement of appropriate hormones may be required as the steroid dose is tapered.
- b. For **Grade 3-4** events, treat with an initial dose of IV corticosteroids followed by oral corticosteroids. When symptoms improve to Grade 1 or less, steroid taper should be started and continued over no less than 4 weeks. Replacement of appropriate hormones may be required as the steroid dose is tapered.

• Hyperthyroidism or Hypothyroidism:

Thyroid disorders can occur at any time during treatment. Monitor patients for changes in thyroid function (at the start of treatment, periodically during treatment, and as indicated based on clinical evaluation) and for clinical signs and symptoms of thyroid disorders.

- a. Grade 2 hyperthyroidism events (and Grade 2-4 hypothyroidism):
 - i. In hyperthyroidism, non-selective beta-blockers (e.g. propranolol) are suggested as initial therapy.
 - ii. In hypothyroidism, thyroid hormone replacement therapy, with levothyroxine or liothyronine, is indicated per standard of care.
- b. Grade 3-4 hyperthyroidism
 - i. Treat with an initial dose of IV corticosteroid followed by oral corticosteroids. When symptoms improve to Grade 1 or less, steroid taper should be started and continued over no less than 4 weeks. Replacement of appropriate hormones may be required as the steroid dose is tapered.

• Hepatic:

- a. For **Grade 2** events, monitor liver function tests more frequently until returned to baseline values (consider weekly).
 - i. Treat with IV or oral corticosteroids
- b. For Grade 3-4 events, treat with intravenous corticosteroids for 24 to 48 hours.
- c. When symptoms improve to Grade 1 or less, a steroid taper should be started and continued over no less than 4 weeks.

• Renal Failure or Nephritis:

- For Grade 2 events, treat with corticosteroids.
- For Grade 3-4 events, treat with systemic corticosteroids.
- When symptoms improve to Grade 1 or less, steroid taper should be started and continued over no less than 4 weeks.
- **Neurological Toxicities:** Ensure adequate evaluation to confirm etiology and/or exclude other causes.
 - a. For Grade 2 events, withhold pembrolizumab.
 - b. For Grade 3-4 events, permanently discontinue pembrolizumab.
 - c. Administer corticosteroids based on severity of the AE.
- Myocarditis: Ensure adequate evaluation to confirm etiology or exclude other causes.
 - a. For Grade 1 events, withhold pembrolizumab.
 - b. For Grade 2-4 events, permanently discontinue pembrolizumab.
 - c. Administer corticosteroids based on severity of the AE.
- **Exfoliative Dermatologic Conditions:** Ensure adequate evaluation to confirm etiology or exclude other causes.
 - a. For **suspected** SJS (Stevens-Johnson syndrome), TEN (toxic epidermal necrolysis), or DRESS (Drug reaction with eosinophilia and systemic symptoms), withhold pembrolizumab.
 - b. For confirmed SJS, TEN, or DRESS, permanently discontinue pembrolizumab.
 - c. Administer corticosteroids based on severity of the AE.
- **Management of Infusion Reactions**: Signs and symptoms usually develop during or shortly after drug infusion and generally resolve completely within 24 hours of completion of infusion.

Table 4 below shows treatment guidelines for subjects who experience an infusion reaction associated with administration of pembrolizumab (pembrolizumab). Management of rituximab or obinutuzumab infusion reactions will be performed according to institutional practice and investigator judgment.

Table 4 Pembrolizumab Infusion Reaction Dose Modification and Treatment Guidelines

NCI CTCAE Grade	Treatment	Premedication at
		Subsequent Dosing

Grade 1 Mild reaction; infusion interruption not indicated; intervention not	Increase monitoring of vital signs as medically indicated until the participant is deemed medically stable in the opinion of the investigator.	None
indicated		
Grade 2	Stop Infusion.	Participant may be
Requires therapy or	Additional appropriate medical therapy may include	premedicated 1.5h (\pm 30
infusion interruption	but is not limited to:	minutes) prior to infusion of
but responds promptly	IV fluids	with:
to symptomatic	Antihistamines	Diphenhydramine 50 mg po
treatment (e.g.,	NSAIDs	(or equivalent dose of
antihistamines,	Acetaminophen	antihistamine).
NSAIDs, narcotics, IV	Narcotics	Acetaminophen 500-1000
fluids); prophylactic	Increase monitoring of vital signs as medically	mg po (or equivalent dose of
medications indicated	indicated until the participant is deemed medically	analgesic).
for ≤ 24 hrs	stable in the opinion of the investigator.	
	If symptoms resolve within 1 hour of stopping drug	
	infusion, the infusion may be restarted at 50% of the	
	original infusion rate (e.g. from 100 mL/hr to 50	
	mL/hr). Otherwise dosing will be held until symptoms	
	resolve and the participant should be premedicated for the next scheduled dose.	
	Participants who develop Grade 2 toxicity despite	
	adequate premedication should be permanently discontinued from further study drug intervention	
Grades 3 or 4	Stop Infusion.	No subsequent dosing
Grade 3:	Additional appropriate medical therapy may include	No subsequent dosing
Prolonged (i.e., not	but is not limited to:	
rapidly responsive to	Epinephrine**	
symptomatic	IV fluids	
medication and/or	Antihistamines	
brief interruption of	NSAIDs	
infusion); recurrence	Acetaminophen	
of symptoms	Narcotics	
following initial	Oxygen	
improvement;	Pressors	
hospitalization	Corticosteroids	
indicated for other	Increase monitoring of vital signs as medically	
clinical sequelae (e.g.,	indicated until the participant is deemed medically	
renal impairment,	stable in the opinion of the investigator.	
pulmonary infiltrates)	Hospitalization may be indicated.	
Grade 4:	**In cases of anaphylaxis, epinephrine should be used	
Life-threatening;	immediately.	
pressor or ventilatory	Participant is permanently discontinued from	
support indicated	further study drug intervention.	
	equipment should be available at the bedside and a physician rea	dily available during the period of
drug administration.	· ·	
	please refer to the Common Terminology Criteria for Ad	lverse Events v5.0 (CTCAE) at

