4.2.1.2 Dose Modification (Escalation/Titration/Other)

Adverse events (both non-serious and serious) associated with pembrolizumab exposure may represent an immunologic etiology. These adverse events may occur shortly after the first dose or several months after the last dose of treatment. Pembrolizumab must be withheld for drug-related toxicities and severe or life-threatening AEs as per Table 3 below. See Section 5.6 for supportive care guidelines, including use of corticosteroids. Table 3 lists dose modifications for pembrolizumab. Note that dose modification of rituximab, and management of rituximab-related infusion reactions, will follow institutional standard of care and investigator/sub-investigator discretion and is not specified in this protocol.

Table 3 Dose modification and toxicity management guidelines for immune-related AEs associated with pembrolizumab

Toxicity	Hold Treatment For Grade	Timing for Restarting Treatment	Treatment Discontinuation	
Diarrhea/Colitis	Z-3 Toxicity resolves to Grade 0-1 to reduce corticosteroid t		Toxicity does not resolve within 12 weeks of last dose or inability to reduce corticosteroid to 10 mg or less of prednisone or equivalent per day within 12 weeks	
	4	Permanently discontinue	Permanently discontinue	
AST, ALT, or	2	Toxicity resolves to Grade 0-1	Toxicity does not resolve within 12 weeks of last dose	
Increased Bilirubin 3-4		Permanently discontinue (see exception below) ^a	Permanently discontinue	
Type 1 diabetes mellitus (if new onset) or Hyperglycemia	T1DM or 3-4	Hold pembrolizumab for new onset Type 1 diabetes mellitus or Grade 3-4 hyperglycemia associated with evidence of beta cell failure	Resume pembrolizumab when patients are clinically and metabolically stable	
Hypophysitis	2-4	Toxicity resolves to Grade 0-1. Therapy with pembrolizumab can be continued while endocrine replacement therapy is instituted	Toxicity does not resolve within 12 weeks of last dose or inability to reduce corticosteroid to 10 mg or less of prednisone or equivalent per day within 12 weeks	
Hyperthyroidism	3	Toxicity resolves to Grade 0-1	Toxicity does not resolve within 12 weeks of last dose or inability to reduce corticosteroid to 10 mg or less of prednisone or equivalent per day within 12 weeks	
	4	Permanently discontinue	Permanently discontinue	

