Hypothyroidism		Therapy with pembrolizumab can be continued while thyroid replacement therapy is instituted	Therapy with pembrolizumab can be continued while thyroid replacement therapy is instituted	

Protocol v4.0 dated 21 July 2021

Page 19 of 62

Toxicity	Hold Treatment For Grade	Timing for Restarting Treatment	Treatment Discontinuation	
Pneumonitis	2	Toxicity resolves to Grade 0-1	Toxicity does not resolve within 12 weeks of last dose or inability to reduce corticosteroid to 10 mg or less of prednisone or equivalent per day within 12 weeks.	
Fneumonitis	Recurrent grade 2, or grade 3-4	Permanently discontinue	Permanently discontinue	
Renal Failure or Nephritis	2	Toxicity resolves to Grade 0-1	Toxicity does not resolve within 12 weeks of last dose or inability to reduce corticosteroid to 10 mg or less of prednisone or equivalent per day within 12 weeks	
_	3-4	Permanently discontinue	Permanently discontinue	
	1 or 2	Withhold	• Based on severity of AE administer corticosteroids	• Ensure adequate evaluation to confirm
Myocarditis	3 or 4	Permanently discontinue		etiology and/or exclude other causes
	Intolerable/ persistent Grade 2 ^b	Withhold	Based on severity of AE administer corticosteroids	• Ensure adequate evaluation to confirm etiology or exclude other
All Other immune- related AEs	3	Withhold or discontinue based on the event ^c .		causes
	4 or	Permanently discontinue		
	recurrent	-		
	Grade 3			
		severe or Grade 3 drug-related AE that rec gin treatment with Grade 2 AST or ALT, if AS		r equal to 50% relative to baseline

^a For patients with liver metastasis who begin treatment with Grade 2 AST or ALT, if AST or ALT increases by greater than or equal to 50% relative to baseline and lasts for at least 1 week then patients should be discontinued.\

^b Patients with intolerable or persistent Grade 2 drug-related AE may hold study medication at physician discretion. Permanently discontinue study drug for persistent Grade 2 adverse reactions for which treatment with study drug has been held, that do not recover to Grade 0-1 within 12 weeks of the last dose.
^c Events that require discontinuation include but are not limited to: Guillain-Barre Syndrome, encephalitis, Stevens-Johnson Syndrome and toxic epidermal

^c Events that require discontinuation include but are not limited to: Guillain-Barre Syndrome, encephalitis, Stevens-Johnson Syndrome and toxic epidermal necrolysis.

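### Table 3 is laxer than section 4.3.3 on pembrolizumab-related neurological toxicity, nothing ranks one text above the other, and the pointers between them are wrong

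*Combined protocol and SAP*

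**What the plan says.** Section 4.2.1.2 gives Table 3 mandatory force: "Pembrolizumab must be withheld for drug-related toxicities and severe or life-threatening AEs as per Table 3 below". It then sends the reader onward: "See Section 5.6 for supportive care guidelines, including use of corticosteroids".

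Table 3 lists immune-related events by organ and ends with a residual row for all other immune-related events. Neurological toxicity has no row of its own. In the residual row the Grade 2 trigger is an intolerable or persistent event, Grade 3 is withheld or discontinued depending on the event, and Grade 4 or recurrent Grade 3 is a permanent stop. Footnote b qualifies the Grade 2 entry: "Patients with intolerable or persistent Grade 2 drug-related AE may hold study medication at physician discretion". It adds a permanent stop for persistent Grade 2 reactions that were held and "that do not recover to Grade 0-1 within 12 weeks of the last dose". Footnote c gives examples: "Events that require discontinuation include but are not limited to: Guillain-Barre Syndrome, encephalitis, Stevens-Johnson Syndrome and toxic epidermal" necrolysis.

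Section 4.3.3 names neurological toxicity separately. Its Grade 2 instruction is "For Grade 2 events, withhold pembrolizumab", and Grade 3-4 is a permanent discontinuation. The list opens with "Suggested supportive care measures for the management of adverse events with potential immunologic etiology are outlined below". A later paragraph begins "When study interventions are administered in combination, attribution of an adverse event to a single component is likely to be difficult" and goes on to say that, for the events listed, all interventions must be held by the criteria that follow. A note in the same section refers the reader to Table 4 for dose modification.

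**The concern.** Both texts cover events related to pembrolizumab and both direct what happens to the next dose, so for a given event and grade they should give the same answer. For neurological events they do not, and Table 3, which an investigator would naturally open to make a dosing decision, is the more permissive. At stake is a further pembrolizumab dose for a patient with a Grade 2 neurological event that is tolerable and not persistent, although the protocol's event-specific rule withholds that dose. The matter is patient safety and consistent dosing. It does not touch sample size, error rates or the response endpoint.

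**Working it through.** No arithmetic applies. The check sets the two texts side by side, then looks for a ranking rule and follows each pointer.

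**1. Which Table 3 row applies.** With no neurological row, the residual row is the only candidate. Footnote c to that row names Guillain-Barre syndrome and encephalitis, which confirms that neurological events belong there.

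**2. Comparison by grade, neurological events.**

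| Event | Table 3, residual row | Section 4.3.3 | Result |
|---|---|---|---|
| Grade 2, tolerable and not persistent | no hold listed | withhold | Table 3 laxer |
| Grade 2, intolerable or persistent | withhold, but discretionary under footnote b | withhold | Table 3 laxer in force |
| Grade 3 | withhold or discontinue, by event | permanently discontinue | Table 3 looser, but can accommodate 4.3.3 |
| Grade 4 | permanently discontinue | permanently discontinue | agree |

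The first line is the clearest difference. The Grade 3 line is weaker: deciding by event leaves room to discontinue, and footnote c says that its list is not exhaustive.

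**3. Is there a ranking rule?** Section 4.2.1.2 makes Table 3 mandatory and does not mention the 4.3.3 criteria. Section 4.3.3 introduces its measures as suggested, then says that interventions must be held by its own criteria, then says that for immune-related events they should be held by recommended dose modifications, naming no table. The second statement supports following 4.3.3. None of the three says what to do where 4.3.3 and Table 3 differ.

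**4. Pointers.** Section 4.2.1.2 cites Section 5.6. Section 5 is the trial flow chart and contains only 5.1; the supportive care guidelines are section 4.3.3. The note in 4.3.3 cites Table 4, which covers infusion reactions; the immune-related rules are in Table 3. Both pointers are wrong.

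**5. Restarting.** The neurological entry in 4.3.3 gives no recovery grade or time limit. Footnote b of Table 3 supplies both (Grade 0-1, 12 weeks from the last dose). The texts therefore have to be read together, which is why the broken pointers matter.

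**6. Another event with a difference.** For Grade 2 myocarditis, Table 3 says withhold and 4.3.3 says permanently discontinue. This is sharper than the neurological case, and any general precedence rule will settle it.

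**The case against.** The strongest reply is that the two texts can both be obeyed. Table 3 never orders a dose, so an investigator who follows the specific, stricter rule in 4.3.3 breaches nothing. The mandatory sentence in 4.3.3 points the same way. Although the section number is wrong, section 4.2.1.2 names the supportive care guidelines, and that heading can be found. The trial is single-center, so differing practice between sites does not arise. The faulty Table 4 reference sits in a note about events judged unrelated, so it has little consequence for related neurological events. All of this stands, and it limits the point to a minor one. It does not remove it: the reply protects only the investigator who turns to 4.3.3 and treats it as governing.

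Four stronger readings are tempting, and the documents do not support them:

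- **Contradictory orders.** A reader might infer that the neurological rules cannot both be followed. They can.
- **Section 4.3.3 is only advisory.** The word suggested introduces supportive care measures, and the section then uses mandatory wording for the listed events.
- **The mandatory sentence lapses when pembrolizumab is given alone.** A reader might take its opening words about combination administration to exclude such dosing days. The words fit the regimen more naturally, and the neurological instruction itself withholds pembrolizumab with no combination condition. A count of pembrolizumab-only doses would therefore measure nothing relevant.
- **DRESS is a further contradiction.** Section 4.3.3 names it and Table 3 does not, but footnote c is open-ended and silence is not conflict.

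**Conclusion.** The point holds, at minor severity. For pembrolizumab-related neurological toxicity Table 3 is more permissive than section 4.3.3, clearly at Grade 2 and more loosely at Grade 3. No sentence ranks the two, and both pointers between them are wrong. Used alone, Table 3 allows a dose that 4.3.3 withholds.

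The size cannot be put in patients, because the documents give no rate for neurological toxicity. No statistical quantity changes.

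The conclusion rests on placing neurological events in the residual row, which footnote c supports. One note to Table 3 is cut off in the available text. Its readable part concerns severe or Grade 3 events, so the Grade 2 finding does not depend on it, but the Grade 3 comparison is made without it.

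**What to change.** 1. Add a neurological row to Table 3. Grade 2: withhold, restart on recovery to Grade 0-1, permanently discontinue if not recovered within 12 weeks of the last dose. Grade 3-4: permanently discontinue.
2. State that the event-specific rule in 4.3.3 governs wherever it is stricter than Table 3. Tell the sponsor openly that this makes Grade 2 myocarditis a permanent discontinuation, and correct the Table 3 myocarditis row to match (Grade 1 withhold; Grade 2-4 permanently discontinue).
3. In 4.2.1.2 change the Section 5.6 reference to 4.3.3. In the 4.3.3 note change the Table 4 reference to Table 3.

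Naming DRESS in Table 3 is optional tidying, since the precedence sentence would already cover it.

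The cost is one new table row, one corrected row, one sentence and two cross-references in an amendment. Sample size, analysis and data collection are unaffected.

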to Merck Product	Dechallenge	Was Merck product discontinued or dose/exposure/frequency reduced?
(continued)		If yes, did the AE resolve or improve?
(continueu)		If yes, this is a positive dechallenge. If no, this is a negative dechallenge.
		(Note: This criterion is not applicable if: (1) the AE resulted in death or permanent disability; (2) the AE resolved/improved despite continuation of the investigational product; or (3) the trial is a single-dose drug trial); or (4) investigational product(s) is/are only used one time.)
	Rechallenge	Was the subject re-exposed to Merck product in this study?
		If yes, did the AE recur or worsen?
		If yes, this is a positive rechallenge. If no, this is a negative rechallenge.
		(Note: This criterion is not applicable if: (1) the initial AE resulted in death or permanent disability, or (2) the trial is a single-dose drug trial); or (3) investigational product(s) is/are used only one time).
		NOTE: IF A RECHALLENGE IS PLANNED FOR AN ADVERSE EVENT WHICH WAS SERIOUS AND WHICH MAY HAVE BEEN CAUSED BY MERCK PRODUCT, OR IF REEXPOSURE TO MERCK PRODUCT POSES ADDITIONAL POTENTIAL SIGNIFICANT RISK TO THE SUBJECT, THEN THE RECHALLENGE MUST BE APPROVED IN ADVANCE BY THE SPONSOR-INVESTIGATORAS PER DOSE MODIFICATION GUIDELINES IN THE PROTOCOL.
	Consistency with Trial Treatment Profile	Is the clinical/pathological presentation of the AE consistent with previous knowledge regarding Merck product or drug class pharmacology or toxicology?
The assessment o above elements.	f relationship will l	be reported on the worksheets by an investigator who is a qualified physician according to his/her best clinical judgment, including consideration of the
Record one of th	e following	Use the following scale of criteria as guidance (not all criteria must be present to be indicative of Merck product relationship).
Yes, there is a re possibility of Me relationship.		There is evidence of exposure to Merck product. The temporal sequence of the AE onset relative to the administration of Merck product is reasonable. The AE is more likely explained by Merck product than by another cause.

No, there is not a reasonable	Subject did not receive the Merck product OR temporal sequence of the AE onset relative to administration of Merck product is not reasonable OR	
possibility of Merck product relationship	the AE is more likely explained by another cause than the Merck product. (Also entered for a subject with overdose without an associated AE.)	
relationship		

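### For grade 2 myocarditis, Table 3 says withhold pembrolizumab, Section 4.3.3 says stop it permanently, and nothing says which governs

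*Combined protocol and SAP*

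**What the plan says.** Section 4.2.1.2 makes Table 3 binding for withholding pembrolizumab. The table's myocarditis entry has two rows: "1 or 2 Withhold" and then "Myocarditis 3 or 4 Permanently discontinue". The entry states no condition for restarting.

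The myocarditis item in Section 4.3.3 withholds at grade 1 and then says "For Grade 2-4 events, permanently discontinue pembrolizumab". That section introduces its measures as suggestions, but it also says that all interventions have to be held according to the criteria it lists. On restart it says: "If the toxicities do resolve and conditions are aligned with what is defined below, the combination of study therapies may be restarted", at the investigator's discretion.

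The rechallenge row of Table 6 (Section 6.8) covers re-exposure after a serious event that pembrolizumab may have caused, or re-exposure that carries significant added risk. In those cases "THEN THE RECHALLENGE MUST BE APPROVED IN ADVANCE BY THE SPONSOR-INVESTIGATORAS PER DOSE MODIFICATION GUIDELINES IN THE PROTOCOL".

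**The concern.** An investigator facing grade 2 myocarditis finds a different instruction depending on which section is opened. Both stop the drug immediately, so the first response is the same. They part on what follows. Section 4.3.3 ends pembrolizumab for good. Table 3 sets withholding against permanent discontinuation, which implies that a withheld drug may be resumed. An investigator relying on the table could therefore seek to restart a checkpoint inhibitor after a cardiac immune toxicity that the other section treats as a permanent stop. What is at stake is the safety of that patient, not the trial's inference.

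**Working it through.** The plan states no figure to reproduce, so the check is a comparison of texts followed by a bound on exposure.

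**1. Does the grade 1 or 2 row belong to myocarditis?** The table is broken in the supplied text, so this needs an argument. The preceding renal entry has its own grade 2 row ("Renal Failure or Nephritis 2 Toxicity resolves to Grade 0-1") and its own grade 3-4 row. The row in question follows both and comes directly before the row labelled myocarditis. The next entry, for all other immune-related events, has its own rows for grades 2, 3 and 4. No other toxicity can own the row.

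**2. Grade-by-grade comparison.**

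| Grade | Table 3 | Section 4.3.3 | Result |
|---|---|---|---|
| 1 | Withhold | Withhold | Agree |
| 2 | Withhold | Permanently discontinue | Conflict |
| 3 | Permanently discontinue | Permanently discontinue | Agree |
| 4 | Permanently discontinue | Permanently discontinue | Agree |

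**3. Does anything rank the two?** No precedence sentence exists, and both sections use mandatory language. The pointers that should connect them fail. Section 4.2.1.2 says "See Section 5.6 for supportive care guidelines, including use of corticosteroids", but the document as supplied has no Section 5.6. Section 4.3.3 says "Refer to Table 4 for dose modification", but Table 4 covers infusion reactions and has no myocarditis row.

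**4. Is the difference deliberate?** Nothing suggests so. For pneumonitis, both sections permanently discontinue at recurrent grade 2 or at grade 3-4. The myocarditis mismatch looks like an editing slip.

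**5. Size for one affected patient.** Inputs from Section 6.1.6: pembrolizumab every 3 weeks, up to 2 years, maximum 35 infusions. Let the event follow the infusion of cycle k.

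- Section 4.3.3: 0 further infusions.
- Table 3 read alone, only the infusion cap binding: 35 − k. This gives 35 − 1 = 34, 35 − 4 = 31 and 35 − 8 = 27.
- If 2 years means calendar time (104 weeks), a hold uses up slots, because 35 three-weekly doses already span 34 × 3 = 102 weeks. With an added delay of h weeks the next dose falls at week 3k + h, and the number remaining is the smaller of 35 − k and floor((104 − 3k − h)/3) + 1. For k = 1 and h = 4: floor(97/3) + 1 = 32 + 1 = 33.

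| Added delay h (assumed) | k = 1 | k = 4 | k = 8 |
|---|---|---|---|
| 0 weeks | 34 | 31 | 27 |
| 4 weeks | 33 | 30 | 26 |
| 12 weeks | 30 | 27 | 23 |

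These are ceilings for the initial course. They are not expected exposure.

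**The case against.** The strongest reply is that the protocol, read as a whole, already answers the restart question. Section 4.3.3 removes a participant from all study interventions if the toxicity does not resolve or the criteria for resuming are not met. It allows restart only when its own listed conditions are satisfied, and for grade 2 myocarditis the listed condition is a permanent stop. Table 3 offers no competing permission: its renal and pneumonitis grade 2 rows state a recovery criterion for restarting, while its myocarditis row states none. A risky rechallenge also needs advance approval. Harm would require an investigator to infer a permission from Table 3 alone and the approver to miss Section 4.3.3, in a single-center trial.

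Much of this stands. Section 4.3.3 favours no restart, and the safeguards make one less likely. They do not settle the conflict. The restart wording neither mentions nor overrides Table 3, which comes earlier and is mandatory. The Table 6 approval is to follow the protocol's dose modification guidelines, and Table 3 carries that description in its title, so the approver is sent back to texts that disagree.

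The reply is also right about the infusion counts. They measure room left for dosing, not probability of harm. Going beyond cycle 4 requires at least a partial response in Arms A and B, or stable disease with clinical benefit in Arm C. A 12-week added delay puts the next dose 3 + 12 = 15 weeks after the last, beyond the 12-week limit in most other Table 3 rows.

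**Conclusion.** The conflict is real and confined to one grade of one toxicity. For an affected patient the two rules differ by 0 versus at most 34, 31 or 27 further infusions after an event at cycle 1, 4 or 8. Those counts assume that only the infusion cap binds and that the patient otherwise qualifies to continue; they fall to 30, 27 and 23 under a 104-week limit with an assumed 12-week added delay. The documents give no rate of grade 2 myocarditis, so no number of cases is claimed.

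Permanent discontinuation at grade 2 complies with both texts, so the risk is limited to a restart based on Table 3. Confidence in the textual mismatch is high; how often it would lead to a restart is unknown. The point should be corrected because it sits in a live dosing rule for a cardiac toxicity.

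**What to change.** Change the myocarditis entry in Table 3 to: grade 1, withhold; grades 2 to 4, permanently discontinue. This matches Section 4.3.3 and is the only grade 2 rule that already complies with both texts.

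In the same amendment, correct the two cross-references. Section 4.2.1.2 should cite Section 4.3.3 for supportive care. Section 4.3.3 should cite Table 3 for dose modification, keeping Table 4 for infusion reactions.

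The cost is one table entry and two references in a wording amendment at a single center, with no effect on sample size, stopping rules or analysis. The downside is that a patient who recovers from grade 2 myocarditis cannot resume pembrolizumab, which Section 4.3.3 already requires.
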